10.2 Data linkage

We will link to the National Death Index to ascertain deaths and cause of death within the cohort and the National Cancer Statistics Clearing House and/or State Cancer Registers to ascertain newly diagnosed cancers. Major health events requiring hospital admission will be confirmed or identified by linkage to hospital admitted patients' registers in each State where possible within the constraints set by data custodians. Linkage to Medicare Australia will enable capture information about items such as GP consultations, medical tests and medication use. We will link towards the end of 2017 (the end of the current project grant) and approximately 10 years after recruitment began.

11 Sub-studies

11.1 D-Health sub-studies

Participants in D-Health may be invited to participate in smaller sub-studies. Some of these may require telephone or face-to-face interviews. Ethics approval will be sought for these prior to their implementation.

11.2 D-Health Microbiome Project (P2365)

Participants will be randomly selected and invited to participate in the D-Health Microbiome Project (P2365). This involves a separate consent process. Data collected as part as the D-Health Trial (P1519) will be shared with the D-Health Microbiome Project (P2365). This will include all survey and linked data. The link between the microbiome data and the D-Health data will be based on the participant identification number and no identifying information will be shared with the microbiome project.

12 D-Health Trial Database

There will be no hard copy case report forms used in D-Health. Instead, all participant information (eg randomisation code, date of randomisation, adverse events, survey return, blood sampling) will be entered directly into the custom-built D-Health Trial database.

The database will meet ICH-GCP requirements (appendix 2).

13 Assessment of safety

Adverse events monitoring and reporting will comply with QIMR Berghofer Standard Operating Procedure 13

13.1 Definitions

Adverse Event (AE): any untoward medical occurrence in a participant or clinical trial subject administered a medicinal product and which does not necessarily have a causal relationship with this treatment. *An AE can therefore be any unfavourable and unintended sign (including an abnormal laboratory finding), symptom, or disease temporally associated with the use of an investigational medicinal product (IMP), whether or not considered related to the IMP.*

Adverse Reaction (AR): all untoward and unintended responses to an IMP related to any dose administered. *All AEs judged as having a reasonable causal relationship to a medicinal product qualify as adverse reactions. The expression reasonable causal relationship means that there is evidence to suggest a possible, probable or definite causal relationship (see section 1.1 below).*

Unexpected Adverse Reaction: an AR, the nature or severity of which is not consistent with the applicable product information (e.g. investigator's brochure). *When the outcome of the adverse reaction is not consistent with the applicable product information this adverse reaction should be considered as unexpected. Side effects which occur in a more severe form than anticipated are also considered to be unexpected.*

Serious Adverse Event (SAE) or Serious Adverse Reaction (SAR): any untoward medical occurrence or effect that at any dose

- Results in death
- Is life-threatening refers to an event in which the participant was at risk of death at the time of the event; it does not refer to an event which hypothetically might have caused death if it were more severe
- Requires hospitalisation, or prolongation of existing inpatients' hospitalisation
- Results in persistent or significant disability or incapacity

Medical judgement should be exercised in deciding whether an AE/AR is serious in other situations. Important AE/ARs that are not immediately life-threatening or do not result in death or hospitalisation but may jeopardise the participant or may require intervention to prevent one of the other outcomes listed in the definition above, should also be considered serious.

Suspected Unexpected Serious Adverse Reaction (SUSAR): any suspected adverse reaction related to an IMP that is both unexpected and serious. In this case the event is not outlined in Investigator's Brochure (IB).

13.2 Assessing Causality

The assignment of causality should be made using the definitions below.

Relationship	Description
Unrelated	There is no evidence of any causal relationship
Unlikely	There is little evidence to suggest there is a causal relationship (e.g. the event did not occur within a reasonable time after administration of the trial medication). There is another reasonable explanation for the event (e.g. the participant's clinical condition, other concomitant treatment).
Possible	There is some evidence to suggest a causal relationship (e.g. because the event occurs shortly (within 24 hours) after administration of the trial medication). However, the influence of other factors may have contributed to the event (e.g. the participant's clinical condition, other concomitant treatments).
Probable	There is evidence to suggest a causal relationship and the influence of other factors is unlikely.
Definite	There is clear evidence to suggest a causal relationship and other possible contributing factors can be ruled out.

13.3 Monitoring Adverse Events

Phase 1-Intervention phase

During phase 1 of the trial (intervention phase – participants are taking the IMP) monitoring will occur as follows:

- 1. Participants will be provided with a wallet-sized card to show to their general practitioner or other treating physician which asks the doctor to contact the study if the participant is diagnosed with hypercalcaemia, hyperparathyroidism, kidney stones or sarcoidosis (note: vitamin D does not cause hyperparathyroidism or sarcoidosis but these are contraindications to supplementation).
- 2. Participants (or their families) may contact the study to let us know of an adverse event– they will be provided with a fridge magnet including the telephone number to facilitate this.
- 3. Each 12 months after being enrolled participants will be sent a survey in which they will be asked to report hospitalisations and the reasons for them. Participants who don't return the survey will be followed up by telephone, and if they state that they don't plan to complete the survey, we will ask if they have been diagnosed with hypercalcaemia or kidney stones (we will also ask about hyperparathyroidism or sarcoidosis these are not adverse reactions but would be reason to withdraw the participant). We will also ask if they have been hospitalised and the reason for this.
- 4. Towards the end of the intervention phase we plan to link to the National Death Index which will capture deaths that have not already been reported.

Phase 2-Post Intervention phase

During phase 2 of the trial (post-intervention – passive follow-up only) linkage with the National Death Index and Cancer Registers will identify people who have died or have been diagnosed with cancer. Due to the minimal ongoing contact with participants it is possible, but unlikely, that participants will voluntarily contact study staff to advise of an adverse event.

13.4 Recording and Reporting Adverse Events

Phase 1-Intervention phase

At the dose being used, vitamin D supplementation carries very low risk. Thus we plan the following processes:

- 1. Adverse events spontaneously reported by a participant or their doctor during the study.
 - If a participant or their doctor contacts study staff to report an adverse event, an online adverse event reporting form will be completed (see appendix 3).

If the condition hasn't resolved at time of report and the participant continues in the trial, we will contact the participant by phone or email after the next dose to ascertain outcome. If the condition hasn't resolved at the time of report and the participant withdraws, we will contact them by phone or email within the following month.

- The chief investigator will initially assign severity (ie SAE or not) and causality. All AEs will be sent to the study physician for review. If the physician requests further information about the AE, study staff will approach the participant to obtain the necessary information. If the study physician requests changes to the AE severity or causal attribution these will be made before the AE report is submitted to the DSMB and sponsor.
- AEs will be reported biannually to the sponsor, the HREC and the DSMB.
- All SAEs will be reported biannually to the HREC and the DSMB.
- SAEs that are possibly, probably or definitely related to the study medication (hypercalcaemia or kidney stones) will be reported to the sponsor within 24 hours of notification.
- SUSARs will be reported to the HREC, the DSMB and the sponsor within 24 hours of notification

Adverse events captured through annual surveys / falls diaries

- Datatime will provide a monthly upload of survey data. Each month the survey data will be reviewed and a report provided to the sponsor of SAEs that are possibly, probably or definitely related to the study medication (hypercalcaemia or kidney stones).
- All AEs and SAEs that are unrelated or unlikely to be related to the study medication will be reported to the DSMB, the HREC and the sponsor biannually.
- All biannual reports will include an assessment of the statistical significance of any differences between the two study arms.

Adverse event reporting – phase 2 (follow-up phase)

A summary of events (cancer and death) captured through linkage will be provided annually to the HREC and the sponsor. Online adverse event reports will not be completed.

We will have limited further contact with participants during phase 2 (intermittent reports of study findings may be sent), but it is possible that some participants will contact the study to advise of adverse events. These will be managed in the same way as for events reported by participants in phase 1.

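### Section 13.4: the survey and diary list leaves treatment-related SAEs out of the biannual DSMB and HREC reports, at odds with the all-SAE rule for spontaneous reports

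*Protocol*

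**What the plan says.** Protocol section 13.4 sets out phase 1 reporting in two lists.

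The first is headed "Adverse events spontaneously reported by a participant or their doctor during the study". Under it, AEs go twice a year to the sponsor, the HREC and the DSMB. It adds "All SAEs will be reported biannually to the HREC and the DSMB", with no causality limit. Related SAEs also go to the sponsor within 24 hours, and "SUSARs will be reported to the HREC, the DSMB and the sponsor within 24 hours of notification".

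The second is headed "Adverse events captured through annual surveys / falls diaries". It has two routes. For related events: "Each month the survey data will be reviewed and a report provided to the sponsor of SAEs that are possibly, probably or definitely related". Hypercalcaemia and kidney stones are given in brackets as the events meant. For the rest: "All AEs and SAEs that are unrelated or unlikely to be related to the study medication will be reported to the DSMB, the HREC". The sponsor is a recipient here too, and these reports are made twice a year.

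The last bullet of the second list requires every biannual report to assess the statistical significance of differences between the arms.

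Section 13.3 describes the survey as a source of safety data: "Each 12 months after being enrolled participants will be sent a survey in which they will be asked to report hospitalisations". It asks for the cause of each admission as well. Participants who do not return it are telephoned. Those who do not intend to complete it are asked directly about hypercalcaemia, kidney stones and hospitalisation.

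**The concern.** The survey list sorts events by causality and sends the two classes to different recipients. The class withheld from the DSMB and HREC is the one the protocol itself ties to the product's known toxicity: section 3.2 attributes vitamin D toxicity essentially to hypercalcaemia. Because the arm comparison belongs to the biannual reports, an event that appears only in the monthly sponsor report is outside that comparison.

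The consequence reaches section 7.6, which lets the DSMB ask for unblinded data if adverse event reporting suggests that SAE rates differ. That safeguard can respond only to events that are in the reports the DSMB receives. The survey is also the one route in section 13.3 that actively questions every participant about health events. The wallet card and the telephone number rely on someone choosing to contact the study, and linkage to the death index finds deaths only.

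**Working it through.** No arithmetic is needed to establish the gap. The check is to set out the section 13.4 routes by source of event and causality, and then to look for another rule in the protocol that closes it.

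| Source | Class of event | Recipients and timing as written |
|---|---|---|
| Spontaneous | AEs | Sponsor, HREC, DSMB; biannual |
| Spontaneous | All SAEs | HREC, DSMB; biannual |
| Spontaneous | Related SAEs | also sponsor; 24 hours |
| Spontaneous | SUSARs | HREC, DSMB, sponsor; 24 hours |
| Survey or diary | Related SAEs | Sponsor; monthly |
| Survey or diary | Unrelated or unlikely SAEs | DSMB, HREC, sponsor; biannual |
| Survey or diary | Unrelated or unlikely non-serious AEs | DSMB, HREC, sponsor; biannual |
| Survey or diary | Related non-serious AEs | depends on parsing (step 2) |

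**1. Compare the lists.** The spontaneous list pairs a fast report of related SAEs to the sponsor with a biannual report of all SAEs to the HREC and DSMB. The survey list has the counterpart of the first ("a report provided to the sponsor of SAEs that are possibly, probably or definitely related to the study medication") but restricts the second by causality. The related SAE is the cell that loses its DSMB and HREC recipients.

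**2. Parse the biannual survey bullet.** There are three ways to take it.
- The causality limit applies to both AEs and SAEs. Related SAEs and related non-serious AEs are then both outside the biannual report.
- The limit applies to SAEs only. Related non-serious AEs are then inside, and related SAEs are still outside.
- The opening reference to all AEs covers every event, serious ones included, since section 13.1 defines an AE without regard to causality. Related SAEs would then be inside, but the clause about SAEs would do no work.

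The two readings that give the SAE clause a function both leave related SAEs out.

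**3. Test whether another bullet covers them.** The all-SAE rule comes before the survey heading, under spontaneous reports. If it applies only there, the survey SAEs are not covered. If it was meant for every source, the survey bullet's causality limit contradicts it. The SUSAR bullet has the same position and covers unexpected reactions only; given section 3.2, hypercalcaemia is hard to class as unexpected.

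**4. Look elsewhere.** Section 13 refers to an institutional operating procedure, and section 13.5 to the DSMB Terms of Reference. Neither is reproduced. The blood sampling in section 9.6 takes about 600 participants a year, or 600 / 25,000 = 2.4% of the planned sample, and names serum 25D as the assay. It does not specify calcium, so it does not stand in for the survey.

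**5. Size.** Let *s* be the share of related SAEs known only through the survey or diary. The biannual DSMB comparison then contains a fraction 1 − *s* of them. The protocol gives no value for *s*, which could lie anywhere from 0 to 1. If *s* is the same in both arms, the expected rate ratio is unchanged but rests on fewer events, so a true difference is harder to see.

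**The case against.** The best defence is that the lists were meant to be cumulative. The all-SAE bullet carries no limit, and the monthly sponsor report may simply reflect the monthly upload of survey data. Nothing in the section says that the sponsor is the only recipient. The numbering is also irregular in the available text (an item 1 with no item 2), so the nesting of the bullets may not be as the authors intended. Section 7.6 seems to assume that SAE data reach the DSMB unfiltered. All of this makes the cumulative reading possible. It does not explain why the survey bullet then limits SAEs by causality, so the text still needs reconciling.

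Three further objections limit the point, and they stand.

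- A reader might infer that the DSMB would see no hypercalcaemia or kidney-stone cases. The documents do not support this. Each participant carries a card asking doctors to notify the study of exactly these diagnoses, and events reported that way fall under the list that reaches the DSMB.
- A reader might infer that related non-serious survey events are reported to nobody. That follows from only one parsing of the sentence.
- A reader might infer that most related events come through the survey. No figure in the protocol supports that.

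The operating procedure and the Terms of Reference may close the gap in practice. They would not correct the protocol's own rule, which staff preparing the reports would otherwise follow.

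**Conclusion.** The point holds as a defect in the stated reporting rule. For survey and diary events, section 13.4 names only the sponsor as recipient of related SAEs and limits the SAEs in the biannual DSMB and HREC report to those judged unrelated or unlikely to be related. This either conflicts with the all-SAE bullet or is not covered by it. Followed literally, related SAEs known only through the survey are absent from the biannual reports and from their between-arm comparison.

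The conclusion rests on reading the all-SAE bullet under the heading where it stands, and on giving the SAE clause of the survey bullet some effect. The loss is confined to cases not also reported spontaneously or by a doctor, and its size is unknown. The text does not show that the DSMB was in fact deprived of data. The primary and secondary outcomes and the sample size are not affected; what is weakened is independent safety oversight.

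**What to change.** Reconcile the two lists in section 13.4. Reword the biannual survey bullet so that all AEs and SAEs captured through surveys and falls diaries, whatever their assessed causality, are included in the biannual reports to the DSMB, the HREC and the sponsor, and in the between-arm comparison those reports contain. Keep the monthly sponsor report of related SAEs and state that it is additional to the biannual reports. Check that the operating procedure and the DSMB Terms of Reference agree with the new wording.

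Copying the monthly report to the DSMB is not needed to close this gap; even for spontaneous reports, the expedited notice of related SAEs names the sponsor alone. The cost is one reworded bullet and a protocol amendment. The survey data are already reviewed every month, so the extra work is negligible.

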7.6 Randomisation and breaking of codes

Participants will be randomised into one of the two groups. Tablets will be supplied to QIMR Berghofer by an external company that will meet good manufacturing practice (GMP) standards, labelled as A and B. The code will be held by the tablet manufacturing company and a delegate from QIMR Berghofer. When a participant is recruited a QIMR Berghofer staff member will upload the participant ID number into the online randomisation system which will generate the code. Participants will be notified of their tablet allocation after all participants have finished taking tablets and survey collection has been closed. Strategies will be put into place to ensure that study staff, investigators, analysts, and students will not be aware of the study arm tablet assignment until after the primary outcomes have been analysed. The strategy is described in the document: Unblinding Process:_V1 3 December 2019.

The investigators will follow the trial's randomisation and will ensure that the code is broken only in accordance with the protocol. It is recognised that, in the course of clinical practice, it may be necessary for the treating physician to have knowledge of the treatment assignment to ensure the safety of a study subject. This circumstance is extraordinary and will likely impact a minor fraction of the enrolled subjects. In this

situation, the project team will ask the DSMB secretary to provide the treatment assignment to the treating doctor. Any participant who is unblinded will be withdrawn from the study. The DSMB, in the first instance, will monitor all episodes requiring unblinding very carefully and will notify the sponsor of all events.

If adverse event reporting suggests differences in the rate of serious adverse events, the DSMB may request adverse event data that is unblinded.

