14.2 Statistical analysis

We will use intention-to-treat analyses to assess the effect of vitamin D supplementation on all endpoints. Use of the Cox proportional hazards model will allow for variable follow-up lengths and estimation of hazard ratios for mortality and other events obtained from linkage. For outcomes such as falls, fractures and nonmelanoma skin cancer where events can occur more than once, we will use Poisson or negative binomial models (depending on the distribution) to model the number of events. Endpoints that are measured on a continuous scale and that cannot be captured through passive monitoring will be assessed using linear regression models, with analyses to estimate the effects of differential loss-to-follow-up and therefore differences in patient-reported outcomes.

In exploratory analyses we will evaluate effect modification by age, sex, baseline risk factors, dietary calcium intake and predicted baseline vitamin D level (in our pilot data we were able to predict a baseline vitamin D level of less than 50 nmol/L with a C statistic of 0.7). The study has insufficient power for these stratified analyses, but we plan to pool our data with the Vital Study data (and possibly with the FIND data despite its different dose) to substantially increase the available sample size.

Interim analyses will occur after the first linkage (planned for 2017) and after subsequent linkages. Final analysis will be at approximately 5 years after the final participant has completed the intervention phase.

An analysis using Cox Proportional Hazards analysis will be conducted up to the time of change in the formulation of the tablets. This will supplement the final analysis across all time points as presently proposed. In addition, we will carry out some supplementary analyses that are not based on intention-to-treat principles. These will account for compliance and off-trial use of vitamin D (contamination), and we will incorporate time on the old versus the new formulation into these analyses.

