14.3 Criteria for termination of the trial

The Sponsor, Chief Investigator, Ethics Committee (EC) and Regulatory Authorities independently reserve the right to discontinue the study at any time for safety or other reasons. This will be done in consultation with the Sponsor where practical. In the occurrence of premature trial termination or suspension, the abovementioned parties will be notified in writing by the terminator/suspender stating the reasons for early termination or suspension (with the exception of the sponsor's responsibility for notifying the Regulatory Authorities). After such a decision, the Sponsor and the Investigator will ensure that adequate consideration is given to the protection of the subjects' interest. The investigator must review all participating subjects as soon as practical and complete all required records.

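### Section 13.4 sends repeated between-arm significance tests, with deaths not excluded, beyond the DSMB to the sponsor and ethics committee, each of which may stop the trial

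*Protocol*

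**What the plan says.** Section 13.4 sets up twice-yearly adverse-event reporting in the intervention phase and closes the list with a general rule: "All biannual reports will include an assessment of the statistical significance of any differences between the two study arms". It gives no significance level, sets no boundary and excludes no type of event.

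The recipients differ between bullets:

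- Spontaneous reports, adverse events in general: "AEs will be reported biannually to the sponsor, the HREC and the DSMB".
- Spontaneous reports, serious events: "All SAEs will be reported biannually to the HREC and the DSMB". The sponsor is not named here.
- Surveys and falls diaries, events judged unrelated or unlikely to be related: these "will be reported to the DSMB, the HREC and the sponsor biannually", and serious events are included.

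Section 13.1 puts "Results in death" first among the criteria for a serious adverse event, and section 6 makes all-cause mortality the primary outcome. Under section 14.3 the sponsor, chief investigator, ethics committee and regulators "independently reserve the right to discontinue the study at any time for safety or other reasons". The DSMB is not in that list.

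Section 14.2 adds a separate stream: "Interim analyses will occur after the first linkage (planned for 2017) and after subsequent linkages". Section 7.6 says that staff, investigators and analysts "will not be aware of the study arm tablet assignment until after the primary outcomes have been analysed", and that the DSMB may ask for unblinded data if adverse-event reporting suggests a difference in serious-event rates. Section 13.5 refers to a DSMB Terms of Reference document that is not shown.

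**The concern.** Comparative interim results are normally confined to an independent monitoring committee, so that those who run, sponsor or approve a trial are not influenced by chance fluctuations. Here the protocol itself prescribes wider circulation, and in the form most likely to be over-read: a verdict on significance, repeated every six months. Where reports go is fixed by section 13.4; a statistical analysis plan would not normally change it.

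Two things are at stake. First, bodies that can each end the trial may be shown a nominally significant difference in deaths that is due to chance, with no stated standard for judging it. Secondly, knowing which coded arm is ahead can affect conduct even if nobody stops anything. The protocol already uses a more careful model in section 9.6.1, where an independent statistician summarises serum 25D by group without labels. Section 13.4 states no such arrangement for adverse events.

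**Working it through.** **1. The plan's own power figure.** Section 14.1 gives power for total mortality at alpha 0.05 as 0.80 for HR 0.91 and 0.87 for HR 0.90. The number of deaths is not stated, so I solve it from the first row (Schoenfeld, 1:1 allocation, two-sided):

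d = 4(1.960 + 0.842)² / (ln 0.91)² = 3,530 deaths, or 14.1% of 25,000.

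Power at HR 0.90 = Φ(|ln 0.90| × √(3,530/4) − 1.960) = Φ(3.130 − 1.960) = 0.879, against 0.87 stated. The two rows agree. A one-sided 0.05 gives 2,781 deaths and 0.871, so the table does not settle sidedness; two-sided is an assumption below. Either way, the table uses an undivided 0.05.

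**2. Number of reports.** The protocol gives no count. Taking biannual as twice yearly, with about 1 year of recruitment (7.2) and 5 years of intervention each (7.3): 2 × (1 + 5) = 12 from first entry to last tablet, or 2 × 5 = 10 over a five-year span.

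**3. Chance of at least one p<0.05 on deaths under no effect.** With t_k the share of final information at report k, the test statistics have correlation √(t_j/t_k), and the quantity wanted is 1 − P(|Z_k| ≤ 1.96 at every look). I computed it by recursive numerical integration under two timings.

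- *Equally spaced information.* For the column with the final test, the last report is assumed to fall at 40% of final information.
- *Trial calendar.* Uniform entry over one year, a report every 6 months, and final analysis at year 11 (1 + 5 + 5, from 7.2, 7.3 and 14.2). With constant hazard, the report at year 5 has 4.5/10.5 = 43% of final information and the report at year 6 has 5.5/10.5 = 52%. With an assumed 9% yearly growth in hazard, these become 32% and 41%.

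| Timing | Reports | Any report p<0.05 | Adding the final test |
|---|---|---|---|
| Equally spaced | 10 | 19.3% | 22.1% |
| Equally spaced | 12 | 20.8% | 23.4% |
| Calendar, hazard growth 0-9% | 10 | 21.9-22.6% | 24.4-25.5% |
| Calendar, hazard growth 0-9% | 12 | 23.4-24.3% | 25.6-26.8% |

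The ranges are therefore about 19-24% and about 22-27%. The linkage interims of section 14.2 are not counted.

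**4. A strict boundary.** With p<0.001 (|Z| > 3.29) at each of the 10 or 12 reports and 0.05 at the end, the same integration gives an overall type I error of about 5.4-5.5% across these timings. For comparison, a constant boundary holding 5% over equally spaced looks needs a nominal p of about 0.0106 (10 looks) or 0.0097 (12 looks).

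**The case against.** The best case against the point is that section 13.4 describes safety reporting and no mortality analysis. It refers to any differences and names no test of deaths. Until linkage to the National Death Index, planned towards the end of the intervention phase (13.3), the reports hold only deaths that someone has notified. The primary analysis is a separate Cox model on linked data. Levels and boundaries may sit in the DSMB Terms of Reference or the analysis plan, and no passage ties a stopping decision to these tests. All of this stands, and it rules out several stronger readings that a reader might infer.

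- *A dozen unadjusted looks at the primary endpoint.* The count is derived, with 10 to 12 the fair range. The looks are at an incomplete subset of deaths. The lack of adjustment is only silence in this document.
- *A trial type I error above 20%.* The percentages are the chance that some report shows p<0.05. Section 14.3 gives only a general right to discontinue.
- *The sponsor receives every serious event by arm.* The spontaneous-report bullet for serious events omits the sponsor. The HREC, by contrast, is named under both routes.
- *The reports unblind people, contrary to section 7.6.* That section concerns knowledge of treatment assignment. Its provision for the DSMB to request unblinded data implies that routine reports do not identify treatment. No event rates are given to show that hypercalcaemia or kidney-stone counts would reveal the active arm, and the text shown does not establish that the sponsor is the same institute that runs the trial.

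What remains is the routing. A boundary in the Terms of Reference would not by itself stop section 13.4 from sending comparisons to the sponsor and HREC, and incomplete capture of deaths does not remove the multiplicity of repeated testing.

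**Conclusion.** The point holds as a matter of who receives comparative results and in what form. Section 13.4 requires repeated between-arm significance tests, does not exclude deaths, and places them in whole or in part with two bodies outside the DSMB that may each discontinue the trial.

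The size is a false-alarm probability of about 19-24% over the intervention-phase reports, or about 22-27% with the final test. It assumes 10 to 12 reports, reported deaths tested at a two-sided 0.05 each time, no true effect, and the timings shown. It becomes type I error only to the extent that someone acts on a nominal result. I regard this as a cheap improvement. It does not show that the primary analysis is invalid.

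**What to change.** Reword section 13.4 as follows, and align section 14.2 and the DSMB Terms of Reference with it.

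- By-arm comparisons go to the DSMB only, prepared by an independent statistician on the model of section 9.6.1.
- The sponsor and HREC receive pooled counts and the individual expedited reports already provided for.
- Estimates with confidence intervals replace the assessment of statistical significance.
- Mortality is either left out of the biannual comparison or tied to a stated strict boundary consistent with the DSMB Terms of Reference. One example is a Haybittle-Peto rule of p<0.001 at each report with 0.05 kept for the final analysis, giving an overall type I error of about 5.4-5.5%.

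The cost is a short amendment. The sponsor and HREC lose routine by-arm tables while the trial runs. Because the final test stays at 0.05, the loss of power is negligible.
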